 - c. *H2_c: Relative to historical matched controls drawn from previous years of the program, participants receiving sessions will demonstrate greater reductions in HIV sexual risk behavior.*
- 3) **Secondary Aim:** Estimate the effect of MoodGym on the uptake/adherence to ART and PrEP among HIV-positive and HIV-negative participants, respectively.
 - a. *H3_a: Increased attendance to sessions will be associated with lower comorbid depression scores which, in turn, will be associated with increased likelihood of ART medication uptake and/or adherence for HIV-*

positive participants as well as increased likelihood of PrEP uptake and/or adherence for HIV-negative participants.

INTRODUCTION

[figure not shown]
Background

Each year, 70% of new HIV infections in the United States occur with MSM,¹ and use is identified as a major driving force in the continued HIV/AIDS pandemic affecting MSM communities.² Though studies have consistently demonstrated associations between use and HIV transmission among MSM,^{3,4} recent research has further illustrated that depression is likely an under-recognized mechanism in the /HIV link, statistically both mediating and moderating the link between use and engagement in sexual risk behaviors.⁵ Further, depression is an obstacle to medication adherence for both HIV-positive and HIV-negative MSM; depression has been associated with reduced adherence to ART medication,^{6,7} and MSM in the iPrex study with the highest levels of depression also demonstrated the lowest levels of PrEP adherence,⁸ highlighting the important effects of depression on biobehavioral efforts to limit HIV transmission among MSM.

STUDY DESIGN

This study is a single-arm, non-randomized pilot study. Eligible participants are newly enrolled Getting Off service program participants who will be invited to participate in the study during their enrollment, and can enroll in the study at any time during their first two weeks of program participation (see Figure 1).

Figure 1: Study Design “Depression Intervention to Optimize Methamphetamine Treatment Outcomes among Gay and Bisexual Men”

Study activities will take place contemporaneously with participation in the service program (i.e., participants enroll during their first or second week of Getting Off, and

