 - a. Addresses unwelcome, unhealthy, or intrusive thoughts, and demonstrates how some thoughts can help you overcome mental health symptoms. Discusses how to improve self-esteem by changing thought patterns.
4. Unwarping Module
 - a. Introduces the idea of “warpy” thoughts, including false impressions that one must be perfect, that one can control all things, or that one is worthless if they are criticized.
5. Destressing Module
 - a. Discusses means and strategies to reduce stress, which can have important impacts on depression and anxiety symptoms, and mental health more generally.
6. Relationships Module
 - a. Discusses how relationships can both benefit or worsen one's mental health, and how to monitor and maintain healthy relationships.
7. Workbook
 - a. Contains all quizzes and tests the participant encounters during each of the above sessions. If a participant would like to retest themselves on some dimension (e.g., depression, anxiety, warpy thoughts), they can revisit the assessment in the Workbook section, and receive an updated score in real time.

Each MoodGym session will last up to one hour and will begin with the brief CESD-R assessment, administered by the Study Counselor via the same computer as the MoodGym intervention, followed by one of the five online modules, which are self-contained and guide the participant through all intervention content. Online modules include quizzes, videos, characters, interactive activities, informational content, personal stories, workbook activities, and content summaries. Sessions can also include interactions with the Study Counselor, as much or as little as the participant chooses to initiate, including supportive feedback, guidance, help, and encouragement on activities.

Incentive Schedule

All incentives will be paid in gift cards, no cash will be given. The total amount a participant can earn for participating in the study is \$70. Participants can earn \$10 for each session they attend, up to seven session, at the conclusion of each session. After each gift card is dispensed, participants will be asked to sign a sheet, specific only to them, indicating they have received the incentive payout.

Timeline

Table 1. Proposed Timeline of Study Activities

Study Activities	Month	Year 1											
		Q1			Q2			Q3			Q4		
		1	2	3	4	5	6	7	8	9	10	11	12
Obtain IRB Approval		X	X	X									
Hire/Train Study Counselor			X	X									
Enroll 42 MA-Using MSM (6/mo)					X	X	X	X	X	X	X		

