Specific statistical analyses will be chosen based on the distributional properties of the variables being analyzed; sociodemographics or other variables found to significantly influence primary outcomes may be tested for inclusion as statistical controls and/or bases for contingency analyses. The outcome of primary analytical interest, i.e., engagement in HIV sexual risk behaviors, is most amenable to analyses employing the negative binomial or logistic link functions, for count and dichotomous operationalizations, respectively. Descriptive statistics will be provided for all variables, and inferential models related to Specific Aim 2 will assume three complementary but parallel analytical approaches. First (H2_a), an observed treatment effects dosage response analysis will test for observed associations between attendance to the weekly sessions and reductions in both the magnitude (negative binomial) and/or likelihood (logistic) of engagement in HIV sexual risk behaviors [note: sexual risk behavior data is gathered during standard *Getting Off* procedures]; analyses will be double-robustly estimated to ensure proper model specification.¹¹ Second (H2_b), the same model will be estimated, but will further include participants' CESD-R depression scores both as a main effect, as well as in a statistical interaction term with the number of sessions attended. Planning such a nested analysis allows for full specification of the effects of depression, both directly and in response to the intervention. Third (H2_c), participants' HIV sexual risk behavior outcomes will be statistically contrasted against those same outcomes from a group of historical matched controls sampled from the program (2009-2017) and matched using either caliper or nearest neighbor algorithm (based on method of best fit)¹² using participant age, race/ethnicity, HIV status, and the severity of their use. The proposed Secondary Aim will be tested using the Bernoulli family and logistic link function, where uptake or satisfactory (i.e., $\geq 85\%$) adherence to ART/PrEP during the course of the intervention will be coded a "1", "0" otherwise, and regressed on intervention exposure and/or CESD-R depression scores.

Missing Data

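### The Secondary Aim is stated by HIV status, but its logistic model codes one combined ART/PrEP outcome and names no HIV-status term; if pooled, its coefficients can be biased in either direction.

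*Combined protocol and SAP*

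**What the plan says.** In the list of specific aims, the Secondary Aim is to "Estimate the effect of MoodGym on the uptake/adherence to ART and PrEP among HIV-positive and HIV-negative participants, respectively". H3_a keeps the two groups apart: it predicts better ART uptake or adherence in HIV-positive men, and it ends "positive participants as well as increased likelihood of PrEP uptake and/or adherence for HIV-negative participants".

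The analysis is described at the end of Statistical Considerations, Statistical Analyses:

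- Model: "The proposed Secondary Aim will be tested using the Bernoulli family and logistic link function".
- Outcome: uptake, or satisfactory (at least 85%) "adherence to ART/PrEP during the course of the intervention will be coded a" 1, and 0 otherwise.
- Regressors: "and regressed on intervention exposure and/or CESD-R depression scores".

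Two other statements in that section bear on the point. A general clause says that "sociodemographics or other variables found to significantly influence primary outcomes may be tested for inclusion as statistical controls and/or bases for contingency analyses". The matched comparison for H2_c uses HIV status as a matching variable: "using participant age, race/ethnicity, HIV status, and the severity of their use". HIV status is therefore available. The ART/PrEP form is also described under Assessments as covering both HIV-positive and HIV-negative men.

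**The concern.** HIV status decides which drug is counted in the outcome. Starting or adhering to ART after a diagnosis and starting or adhering to PrEP without infection are different behaviours, and nothing in the documents suggests that they succeed equally often. An analyst who follows the written specification would fit one regression to a mixture of the two.

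If men of one HIV status also attend more sessions, or have different CESD-R scores, HIV status confounds the coefficient of interest. An attendance coefficient could then suggest a benefit or a harm of MoodGym that exists in neither group. A confounded CESD-R coefficient would misstate the second step of the pathway in H3_a, from depression to medication use. The pooled coefficient would also answer neither the ART question nor the PrEP question that the aim poses.

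**Working it through.** **The plan's own figure.** Table 1 gives "Enroll 42 MA-Using MSM (6/mo" with seven months marked: 6 × 7 = 42, which agrees. The plan gives no power, significance level or effect size for this aim, so there is no further figure to reproduce.

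**Inputs from the documents.** N = 42. Exposure runs from 0 to 7 sessions (Incentive Schedule).

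**Inputs assumed.** These are the share of HIV-positive men (s), the success rates for ART (pA) and PrEP (pP), and mean sessions in HIV-positive (mA) and HIV-negative (mP) men. Sessions are taken as binomial(7, m/7). MoodGym has no effect in either group.

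**Why both differences are needed.** Under these assumptions the pooled success probability at x sessions is

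P(x) = w(x)·pA + [1 − w(x)]·pP,

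where w(x) is the share of HIV-positive men among those with x sessions, and

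w(x)/[1 − w(x)] = [s/(1 − s)] · (mA/mP)^x · [(7 − mA)/(7 − mP)]^(7 − x).

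If pA = pP, P(x) is constant. If mA = mP, w(x) = s and P(x) is again constant. A false slope appears only when both differ.

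**One worked case:** s = 0.5, 80% vs 40% success, 4.5 vs 3.5 sessions.

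- At x = 0 the odds are (2.5/3.5)^7 = 0.095, so w = 0.087 and P = 0.40 + 0.40 × 0.087 = 0.435.
- At x = 7 the odds are (4.5/3.5)^7 = 5.81, so w = 0.853 and P = 0.40 + 0.40 × 0.853 = 0.741.

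Success appears to rise from 43% to 74% with attendance, although attendance does nothing in either group.

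**Large-sample pooled odds ratio per session** (true value 1.00; s = 0.5; HIV-positive vs HIV-negative):

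| ART vs PrEP success | 4 vs 4 sessions | 4.5 vs 3.5 | 5 vs 3 | 3.5 vs 4.5 |
|---|---|---|---|---|
| 80% vs 80% | 1.00 | 1.00 | 1.00 | 1.00 |
| 80% vs 60% | 1.00 | 1.13 | 1.21 | 0.88 |
| 80% vs 40% | 1.00 | 1.25 | 1.40 | 0.80 |
| 80% vs 20% | 1.00 | 1.38 | 1.69 | 0.72 |

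With 30% or 70% HIV-positive, the case of 80% vs 40% and 5 vs 3 sessions gives 1.33 and 1.40.

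**Rejection rate at N = 42 with no true effect** (two-sided Wald test at 5%, half HIV-positive, 3,000 to 4,000 simulated cohorts per case; repeat runs agreed to within about 2 percentage points):

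| ART vs PrEP success | Mean sessions | Without HIV status | With HIV status |
|---|---|---|---|
| 80% vs 80% | 5 vs 3 | 4% | 4% |
| 80% vs 40% | 4 vs 4 | 4% | 4% |
| 80% vs 60% | 4.9 vs 4.2 | 6% | 4% |
| 80% vs 40% | 4.9 vs 4.2 | 9% | 4% |
| 80% vs 20% | 4.9 vs 4.2 | 16% | 4% |
| 80% vs 40% | 5.25 vs 3.85 | 23% | 4% |
| 80% vs 20% | 5.25 vs 3.85 | 48% | 4% |

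These runs use attendance as the regressor. The same reasoning applies to CESD-R, but no size was computed for it.

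**Power with balanced attendance.** At a true odds ratio of 1.7 per session, power without and with the HIV-status term is 40% and 42% (80% vs 60% success), 35% and 40% (80% vs 40%), and 25% and 34% (80% vs 20%).

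**The case against.** The strongest reply is that pooling is inferred. The Statistical Analyses section gives a family, a link, a coding rule and regressors; it never says that both groups enter one fit. The aim is worded group by group, and the combined ART/PrEP label could be shorthand for one rule applied to each group in turn. If two models are fitted, the confounding disappears. This stands as a limit on certainty, but it does not remove the need for a change, because the section names neither stratification nor an HIV-status term and a reader would naturally fit one model.

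A second reply is the general covariate clause, which permits controls and contingency analyses and does not exclude HIV status. It is optional, however, and its trigger is influence on the primary outcomes; the section names sexual risk behaviour as the outcome of primary interest. HIV status could predict medication use strongly and never meet that trigger.

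A reader might go further and infer that any link between HIV status and attendance or depression would show up as a MoodGym effect. The documents do not support that:

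- Bias also needs unequal success rates; with 80% in both groups the pooled odds ratio is 1.00 whatever the attendance gap.
- It can point towards harm as well as benefit.
- A CESD-R coefficient is an association with depression and is not itself an effect of MoodGym.
- Nothing in the documents shows that attendance or CESD-R differs by HIV status.

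**Conclusion.** The point holds in a conditional form. The specification does not match the aim: two groups and two drugs in the aim, one combined outcome without HIV status in the model. Fitted as it naturally reads, it gives biased coefficients if HIV status is related both to success and to attendance or CESD-R. Every rate and session mean behind the size is an assumption, and the result runs from no inflation (equal success or equal attendance) to about one false rejection in two trials (80% vs 20% success and a gap of 1.4 sessions). The large end should not be read as the expected result. In none of these cases did the HIV-status term raise the error rate. For a secondary aim in a single-arm pilot, this is a correction that should be made; it does not threaten the study's main purpose.

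**What to change.** In Statistical Analyses, make HIV status a mandatory main effect in the Secondary Aim logistic model, and say that it does not depend on the general covariate clause. Report ART results in HIV-positive men and PrEP results in HIV-negative men separately, as the aim is worded, and label them descriptive and imprecise. An even split would leave only 42/2 = 21 men per group.

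An exposure-by-status interaction or Firth penalisation may be added, but neither is needed to resolve the point.

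The cost is a sentence or two in the plan and one extra model parameter. No new data are needed, since HIV status is already used for the H2_c matching.

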complete the 5 sessions over the remaining 6-7 weeks). If participants complete all five MoodGym modules prior to the 8-week endpoint, they will be offered the chance to revisit prior module(s); assessments and incentives will continue as scheduled. Getting Off program evaluation data from study participants will be matched and compared with historical program evaluation data to assess the impact of the MoodGym intervention on the Getting Off program outcomes through an observed treatment effects analysis.

MoodGym

MoodGym is a seven module computer-optimized, evidenced-based intervention for adults with depression and/or anxiety symptoms. Though MoodGym modules can be taken by participants without assistance, evidence suggests results may be improved by applying in a more structured setting. In this pilot study, MoodGym will be delivered with support and guidance from a trained Study Counselor. Each week participants will be asked to attend one one-hour individual appointment with the Study Counselor to complete a MoodGym module, for up to seven weeks.

Phone Call After One Missed Session of MoodGym

The SC will monitor participant attendance and conduct a phone call to any participant who does not attend a scheduled session, to reschedule.

SELECTION AND ENROLLMENT OF PARTICIPANTS

Inclusion Criteria

- A participant enrolled in the Getting Off service program at Friends Community Center; and,
- Within his first or second week in the program

Exclusion Criteria

- Not a participant in his first or second week of the Getting Off service program at Friends Community Center

STUDY PROCEDURES

Recruitment and Enrollment

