MoodGym Implementation					X	X	X	X	X	X	X	X	X
Data Cleaning & Analysis													X
Begin Publication & Dissemination													X

STATISTICAL CONSIDERATIONS

Assessments

1. Center for Epidemiologic Studies Depression Scale (Revised). The Center for Epidemiologic Studies Depression Scale (Revised) [CESD-R]⁹ is a widely used depression assessment which consistently shows strong psychometric properties and concurrent validity with clinical diagnostic instruments.¹⁰ The CESD-R will be administered at the start of each session.

2. ART and PrEP Uptake and Adherence. Administered at baseline enrollment in the pilot study and 3-month follow-up only. The ART and PrEP Uptake and Adherence form briefly queries HIV-positive and HIV-negative participants as to whether they have begun and/or adhered to a prescribed ART or PrEP regimen in the past 3 months.

Statistical Analyses

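### The Secondary Aim model does not say which CESD-R score enters, specifies no first-session adjustment, and leaves the attendance-to-depression step of H3_a without a model

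*Combined protocol and SAP*

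**What the plan says.** The Secondary Aim (H3_a) sets out a chain: "Increased attendance to sessions will be associated with lower comorbid depression scores which, in turn, will be associated with increased likelihood of ART" uptake or adherence in HIV-positive men, and likewise PrEP in HIV-negative men.

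Statistical Analyses gives one model for this aim. It is logistic, with uptake or at least 85% adherence coded 1, "regressed on intervention exposure and/or CESD-R depression scores". No time point, first-session score, change score or trend is named, and there is no model with CESD-R as the outcome.

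On measurement, the Assessments section states: "The CESD-R will be administered at the start of each session". The MoodGym Intervention section places that assessment ahead of the module, so every man who attends at all has a score taken before his first module.

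On who is enrolled, beyond being in the program the inclusion criterion is "Within his first or second week in the program", and the only exclusion is "Not a participant in his first or second week of the Getting Off service program at Friends Community Center". No level of depression is required, although MoodGym is described as an "evidenced-based intervention for adults with depression and/or anxiety symptoms".

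**The concern.** H3_a is about depression falling. A regression of adherence on a CESD-R score with no starting value compares men who score low with men who score high. Some low scorers will have improved, and others will have scored low from the outset. The Background already reports that depression goes with poorer ART and PrEP adherence, so some association is to be expected across men with a mix of symptom levels even if no score moves during the study.

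The and/or wording adds to this. Read one way, it permits a model with CESD-R alone, in which MoodGym does not appear. Under any reading, the first link of the chain has no stated analysis. At stake is whether the reported result for the Secondary Aim bears on H3_a, or only restates an association that the Background takes as known.

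**Working it through.** **Setting the sections side by side**

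| H3_a needs | The plan provides |
|---|---|
| Attendance associated with lower CESD-R | No model |
| Lower CESD-R associated with uptake/adherence | Logistic model; CESD-R optional through and/or, time point not stated |
| A fall distinguished from a low starting score | First-session CESD-R collected, not assigned to the model |

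Two other sentences might seem to fill the gap. Statistical Analyses allows extra covariates, but they are optional, chosen from the data, and tied to the primary outcomes. The data collection section says CESD-R trends are assessed, but no trend term is carried into a model. Neither supplies the missing term.

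One consequence follows from the schedule alone. A man who attends once has only a score taken before any module. The model as written would accept that score as his H3_a predictor.

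**The plan's own figure.** Table 1 plans 6 men per month over 7 marked months: 6 × 7 = 42, as stated. No alpha, power, effect size or CESD-R standard deviation is given.

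**Illustration of size.** These inputs are assumptions, not from the documents:
- MoodGym has no effect on CESD-R.
- Adherence depends only on first-session CESD-R, with odds ratio (OR) 0.67 or 0.5 per SD, and is 50% at mean depression.
- The correlation r between first and last score is 0.4, 0.6 or 0.8.
- Attendance is uniform on 1 to 7 sessions and unrelated to the scores.
- The test is a two-sided 5% Wald test, with 2,000 simulated trials per row at n = 42.

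If the last score equals r times the first score plus noise, its log odds ratio without adjustment should be about r × ln(OR), so the last-score odds ratio is about OR^r. For example, 0.67^0.4 = 0.85 and 0.5^0.8 = 0.57. The simulated medians agree closely:

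| r | OR, first score | OR^r | Last score, unadjusted: OR | Rejected | With first score added: OR | Rejected |
|---|---|---|---|---|---|---|
| 0.4 | 0.67 | 0.85 | 0.85 | 6.4% | 1.02 | 3.9% |
| 0.4 | 0.5 | 0.76 | 0.75 | 11.6% | 1.00 | 5.0% |
| 0.6 | 0.67 | 0.79 | 0.76 | 9.5% | 0.98 | 4.0% |
| 0.6 | 0.5 | 0.66 | 0.65 | 20.8% | 1.00 | 4.0% |
| 0.8 | 0.67 | 0.73 | 0.72 | 15.4% | 0.99 | 4.8% |
| 0.8 | 0.5 | 0.57 | 0.56 | 32.7% | 1.01 | 4.9% |

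At n = 400 (1,000 trials per row) the unadjusted model rejects in 35.9% to 100% of trials and the adjusted model in 4.2% to 5.2%. The unadjusted association is therefore not a small-sample artifact. All rows include attendance as a model term, and all treat every man as having a distinct last score, which a one-session man does not have.

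**The case against.** The strongest reply is that this is an underspecified secondary analysis in a 42-man pilot whose outcome of main interest is sexual risk behavior. The text refers to CESD-R scores without a time point and does not rule out a first-session score. That stands: a reader might infer that the plan excludes baseline adjustment, or that the study cannot tell improvers from men who scored low throughout. The documents show only that the model does not specify the term; the data to do so are collected.

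A reader might also infer that the plan would declare H3_a supported on the CESD-R/adherence association alone. No decision rule says so, and H3_a has a first link that this association does not meet. What remains is that the first link has no model.

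Nor do the documents support the inference that the whole CESD-R coefficient would be spurious. The illustration removes the association on adjustment because it assumes adherence depends only on the first-session score. At its low end the rejection rate is 6.4%, close to nominal.

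Broad eligibility may look like the fault. It is not: H2_b needs a range of depression scores, and an average over all program entrants is a legitimate target. The documents give no share of symptomatic men, so no dilution can be calculated.

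Two further objections stand as limits on the remedy. A change-score analysis would drop men by attendance, which is the exposure itself. And adjusting for first-session CESD-R does not deal with a man already adherent at entry; baseline ART/PrEP status, also collected, bears on that more directly.

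**Conclusion.** The concern holds as a gap in specification with a real consequence. As written, the Secondary Aim model could show a CESD-R/adherence association arising from differences present at entry, and the attendance-to-depression step of H3_a is not analyzed at all. Its size cannot be derived from the documents. Under the assumptions above, false rejection at n = 42 ranges from barely above nominal to about one trial in three, depending on how stable CESD-R is and how strongly entry depression relates to adherence.

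It affects the Secondary Aim only and is worth correcting because the correction is nearly free. A reader might infer that baseline adjustment would isolate the effect of MoodGym. It would not: in a single arm running alongside Getting Off, which is itself based on CBT, a fall in CESD-R may come from that program or from natural recovery.

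**What to change.** Amend the Secondary Aim paragraph of Statistical Analyses, using data already scheduled:

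1. Add a model for the first step: regress the last available CESD-R on sessions attended, adjusting for first-session CESD-R.
2. In the adherence model, replace the and/or wording with exposure and last CESD-R together, adjusting for first-session CESD-R.
3. Keep men with only one session in an exposure-to-adherence model adjusted for first-session CESD-R, so that the exposure range is not truncated.
4. Report any analysis of men symptomatic at first session as descriptive only.
5. State that these models separate improvement from low scores at entry but do not attribute improvement to MoodGym.

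The cost is wording plus one or two extra model terms in about 42 men, fewer if ART and PrEP outcomes are modelled separately by HIV status. Men with fewer than two sessions do not inform the CESD-R change step. Each score precedes that day's module, so a man's last score does not reflect his final session; the write-up should say so.

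### The Secondary Aim's single regression cannot test H3_a, which is a mediation hypothesis; with a later CESD-R in the model, the exposure coefficient is only the direct effect

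*Combined protocol and SAP*

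**What the plan says.** In the list of specific aims, the Secondary Aim is to "Estimate the effect of MoodGym on the uptake/adherence to ART and PrEP among HIV-positive and HIV-negative participants, respectively". Its one hypothesis, H3_a, is a chain: "Increased attendance to sessions will be associated with lower comorbid depression scores which, in turn, will be associated with increased likelihood" of uptake or adherence. CESD-R is therefore the intermediate variable.

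The analysis is in Statistical Considerations, under Statistical Analyses: "The proposed Secondary Aim will be tested using the Bernoulli family and logistic link function". Uptake or satisfactory adherence (at least 85%) is coded 1, anything else 0, and this outcome is "regressed on intervention exposure and/or CESD-R depression scores".

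Under Assessments, the timing of the depression measure is: "The CESD-R will be administered at the start of each session". For the ART/PrEP form it is: "Administered at baseline enrollment in the pilot study and 3-month follow-up only". The Secondary Aim text does not say which of the repeated CESD-R scores enters the model, or which coefficient answers H3_a. The design is single-arm and non-randomised, so exposure is observed attendance.

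**The concern.** The aim and the hypothesis ask different questions. The aim asks whether MoodGym is associated with uptake or adherence at all (an overall association). H3_a asks whether an association runs through depression (an indirect effect). The plan offers one regression for both and leaves its predictors open.

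This has two consequences. First, H3_a has no test: its first link, attendance to CESD-R, is not modelled for this aim, and no indirect effect is planned. Second, if the analyst enters both predictors and reads the exposure coefficient as MoodGym's effect, that reading is wrong. The coefficient then holds the mediator fixed. An effect that works through depression could be reported as no effect, and a signal along some other path could be taken as support for H3_a.

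**Working it through.** **1. What each permitted form estimates.** Write a for attendance to CESD-R, b for CESD-R to outcome given attendance, and c′ for attendance to outcome given CESD-R. H3_a concerns the product a × b.

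- Exposure only: the overall association. It says nothing about the route.
- CESD-R only: the depression-outcome association, not adjusted for attendance.
- Both, with a CESD-R taken after sessions begin: b and c′.

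No form yields a, so none yields a × b. H2_b does put CESD-R and its interaction with attendance in a model, but the outcome there is sexual risk behaviour and CESD-R is a predictor, so it does not supply a either.

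**2. Sample size.** The timeline table gives 6 enrolled per month over months 4 to 10: 6 × 7 = 42, which reproduces the stated enrolment. No alpha, power or effect size is given for this aim.

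**3. Simulation.** All effect sizes are assumptions; the documents give none. Sessions are Binomial(7, 0.65), standardised; CESD-R = a × attendance + noise, total SD 1; logit P(outcome) = b × CESD-R + c′ × attendance. Tests are two-sided 5% Wald tests, with 3,000 runs at N = 42 and 60 runs at N = 20,000. The both-links test requires a and b each to be significant.

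| Scenario (a, b, c′) | H3_a | Exposure only, N = 42 | Exposure given CESD-R, N = 42 | Both links, N = 42 | Median exposure coefficient given CESD-R, N = 20,000 |
|---|---|---|---|---|---|
| Full mediation (−0.5, −1.0, 0) | true | 23% | 5% | 61% | 0.00 |
| Partial mediation (−0.5, −1.0, 0.5) | true | 69% | 19% | 57% | 0.50 |
| First link absent (0, −1.0, 0) | false | 4% | 4% | 4% | 0.00 |
| Second link absent (−0.5, 0, 0) | false | 5% | 4% | 4% | 0.00 |
| No effects (0, 0, 0) | false | 4% | 5% | 0.1% | 0.00 |
| Direct only (0, 0, 0.5) | false | 30% | 30% | 0.3% | 0.50 |
| Full mediation plus unmeasured CESD-R/outcome confounder | true | 20% | 5% | 79% | −0.16 |

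The adjusted exposure coefficient does not follow H3_a. It is significant more often when H3_a is false through a purely direct effect (30%) than when H3_a is true (5% or 19%). The both-links test does follow H3_a where there is no unmeasured confounding. In the last row its 79% is inflated: at N = 20,000 the estimated b is −1.29 against a true −1.0.

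**4. Sensitivity of the size.** A second simulation at N = 42 used sessions uniform on 0 to 7, full mediation and a penalised logistic fit. The assumed log-odds were −0.9, −1.2 and −1.6 per SD of CESD-R.

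- Attendance-CESD-R correlation −0.5: exposure is significant in 2-3% of trials in the joint model, against 19%, 27% and 37% exposure-only. The both-links test gives 46-84%.
- Correlation −0.7: 2-3% against 35%, 52% and 69%; both links 34-72%.
- Weak effects (correlation −0.3, log-odds −0.5): 3% joint against 4-5% exposure-only in two runs, so almost no difference.
- Correlation −0.5, HIV-positive and HIV-negative men analysed separately at an assumed 21 each: exposure-only falls to 6-12%.
- Correlation −0.5, participants with no sessions dropped (they have no CESD-R): exposure-only falls to 12-24%.

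**The case against.** A reader might infer something stronger: that the planned model adjusts away the effect it is meant to estimate, and that its exposure coefficient is null exactly when H3_a is true. The documents do not support this, for four reasons.

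- H3_a does not deny a direct effect. Under partial mediation it is true and the coefficient is 0.50. The coefficient is also null when one link or both are missing and there is no direct effect. The zero under a true H3_a needs full mediation and no unmeasured confounding of CESD-R and outcome.
- The wording permits the joint model without requiring it. Exposure alone is equally allowed, and nothing names the joint-model exposure coefficient as the test.
- The joint model is not an error in itself. Its CESD-R coefficient is H3_a's second link, and any mediation analysis needs it.
- The CESD-R score is unnamed. A first-session score precedes the first module and would be a baseline covariate. But that score cannot carry H3_a's chain, which needs depression that attendance has already lowered.

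It can also be said that power is poor whichever model is used, and that this is an associational secondary hypothesis in a pilot. Both are true, and they limit the importance of the point.

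One could read the and/or wording as fitting both models and comparing exposure coefficients. The plan states no such comparison, and with a logistic link the difference is not the indirect effect. Under partial mediation it is 0.87 − 0.50 = 0.37, against a × b = (−0.5) × (−1.0) = 0.50.

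What stands after all this: no first-link model, no indirect effect, no named coefficient and no named CESD-R score.

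**Conclusion.** The point holds in a limited form. Followed as written, the Secondary Aim analysis cannot test H3_a under any reading of its predictors. That conclusion rests on the text and needs no simulation. In the joint form with a post-exposure CESD-R, the exposure coefficient is the direct effect. It is null under full mediation without unmeasured mediator-outcome confounding, it can be non-null when H3_a is false, and it is not the overall effect named in the aim.

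The size of the loss is conditional. A drop from 23% to 5% (or from 19-69% to 2-3%) holds only under the assumed full mediation and strong effects; with weak effects the models barely differ. This should be corrected before analysis, in proportion to a secondary aim of a 42-person pilot.

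**What to change.** Replace the and/or wording with two stated analyses.

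1. **Overall attendance association:** logistic regression of uptake/adherence on attendance and pre-intervention covariates only. First-session CESD-R may be one of them; no later CESD-R enters.
2. **H3_a:** two equations, both adjusted for first-session CESD-R. The first regresses a named later CESD-R score on attendance. The second regresses the outcome on attendance plus that same later score. Judge H3_a by a bootstrap 95% interval for the indirect effect, or by joint significance of the two links.

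State that the exposure coefficient in the second equation is the direct effect and does not test H3_a. Label all results exploratory and associational. Because CESD-R is taken only at sessions, say how participants with fewer than two sessions, who have no later score, are handled.

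The cost is SAP wording and additional models on data already planned. The interval for the indirect effect will be wide at 42 or fewer, and wider still if ART and PrEP are analysed separately. Confounding remains because attendance is not randomised, and a bootstrap interval does not address it.
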